Pola Polatuzumab Vedotin PR Partial Response

R-ICE Rituximab, ifosfamide, carboplatin, etoposide

SAE Serious Adverse Event

SD Stable disease

1.0 OBJECTIVES

1.1 Primary Objectives

Safety Lead-In

 Evaluate the safety and tolerability of polatuzumab vedotin (Pola) added to rituximab, ifosfamide, carboplatin, and etoposide (PolaR-ICE) as first salvage therapy for relapsed or refractory (R/R) diffuse large B-cell lymphoma (DLBCL).

Phase 2

 Evaluate the anti-tumor activity of PolaR-ICE as first salvage therapy for R/R DLBCL as assessed by the complete response rate after 2 cycles.

1.2 Secondary Objectives

- Evaluate the overall response rate to PolaR-ICE as first salvage therapy for R/R DLBCL.
- Evaluate the progression-free and overall survival of patients who received PolaR-ICE as first salvage therapy for R/R DLBCL followed by autologous stem cell transplantation (ASCT) and single-agent Pola consolidation after ASCT.
- Evaluate the CR rate after Pola consolidation among those who were PR at ASCT.
- Evaluate the toxicity of PolaR-ICE salvage therapy and that of Pola consolidation after ASCT.
- Assess the rate of stem cell mobilization and collection failure in patients with R/R DLBCL who receive PolaR-ICE as first salvage therapy.

1.3 Exploratory Objectives

- Assess the kinetics of circulating tumor DNA after PolaR-ICE as first salvage therapy for R/R DLBCL followed by ASCT and single-agent Pola consolidation after ASCT.
- Assess possible biomarkers of response to PolaR-ICE in patients with R/R DLBCL.
- Examine the association between clinical outcomes (response, PFS) and pathological tumor characteristics.
- Examine the association between clinical outcomes (response, PFS) and ctDNA characteristics (mutation profile, kinetics of clearance).

2.0 BACKGROUND

2.1 Introduction/Rationale for Development

2.1.1 Diffuse Large B-cell Lymphoma

Diffuse large B-cell lymphoma (DLBCL) is the most common lymphoma and accounts for 30-40% of newly diagnosed patients with non-Hodgkin lymphoma (NHL), representing the most common lymphoid neoplasm in adults.[9] DLBCL is considered as one of the aggressive type of NHL, with median age 70 years at diagnosis. Although the majority of patients with newly diagnosed DLBCL achieve long-term remissions with rituximab and multi-agent chemotherapy, approximately 30% of patients will experience relapse or progression. At the time of relapsed disease, the treatment approach is based on whether the patient is a candidate for autologous stem cell transplant (ASCT). In patients considered to be transplant eligible, the decision to proceed to ASCT is determined by the response to salvage treatment.[10, 11] The goals of salvage therapy are typically to minimize disease burden and induce remission, providing the best opportunity to benefit from consolidative ASCT.

Various multi-agent salvage regimens incorporating rituximab have been explored in DLBCL patients. A large randomized comparison of the most commonly used salvage regimens demonstrated the equivalence of rituximab combined with either ICE (ifosfamide, carboplatin, etoposide) or DHAP (dexamethasone, cytarabine, cisplatin).[8]

There were no significant differences overall between these regimens, and the combined results supported an overall response rate (ORR) of 63%, with 37% of patients achieving a complete remission (CR of 25%, unconfirmed CR of 12%). The median progression-free survival (PFS) was found to be approximately 1 year, with a 3-year event-free survival of 31% and 3-year overall survival (OS) of 50%. Patients with chemo-sensitive disease who achieved a CR or partial remission (PR) and had adequate stem cell collection were candidates to proceed to ASCT; only 50% of patients were able to undergo ASCT following salvage therapy. The most common reason to not proceed to ASCT was treatment failure to induce remission.

In general, treatment guidelines support ASCT as the treatment of choice for patients with chemo-sensitive relapsed or refractory DLBCL.[10, 11] Patients who are candidates for ASCT should be treated with multi-agent chemotherapy regimens combined with rituximab, such as DHAP, ESHAP (etoposide, methylprednisolone, high-dose cytarabine and cisplatin), GDP (gemcitabine, dexamethasone, and cisplatin), GCD (gemcitabine, carboplatin, dexamethasone), GemOx (gemcitabine and oxaliplatin), ICE or MINE (mesna, ifosfamide, mitoxantrone, etoposide); there is no clear advantage of one regimen over another. Patients achieving remission should then proceed to consolidative ASCT.[10, 11]

Obtaining a positive emission tomography (PET)-negative CR following second-line salvage therapy has been associated with improvement in outcome in relapsed DLBCL patients who proceed to ASCT.[1-3] A meta-analysis, including 300 patients with DLBCL, demonstrated that a positive PET scan pre-ASCT was associated with a significantly shorter PFS interval (random effects hazard ratio 4.3; 95% CI 3.1, 6; p<0.0001).[3] A PET-positive status pre-ASCT resulted in a 4 to 5-fold higher risk for treatment failure versus a PET-negative status. A smaller study evaluating the prognostic value of pre-ASCT PET scanning in relapsed DLBCL patients found a striking difference in long term outcome, with a 3-year PFS of 81% for patients with a negative scan versus 35% for those with a positive scan. This translated into similar 3-year OS findings, with 81% of patients alive with a negative scan versus 39% with a positive scan.[1]

Novel treatment strategies are needed to improve outcomes for relapsed, transplant-eligible DLBCL patients. The goal of treatment in this population is to achieve a high-quality remission that enables subsequent ASCT. The primary unmet need is the failure to achieve a high rate of CR. Achieving a CR with salvage therapy prior to ASCT has been associated with improved long-term outcomes. Chemo-immunotherapy regimens such as RICE or RDHAP result in less than half of patients achieving CR; adding a novel agent with demonstrated activity in relapsed DLBCL to these regimens has the potential to improve outcomes.

2.1.2 Polatuzumab vedotin

Polatuzumab vedotin (Pola) is an ADC with a monomethyl auristatin E (MMAE) payload directed against CD79b, a part of the B-cell receptor complex that is ubiquitously expressed on B cells. Pola has been studied in B-cell NHL (B-NHL) and CLL as a single agent, and in multiple Pola-based combination studies in patients with B-NHL. The initial phase I dose-escalation study enrolled 95 patients with R/R NHL or CLL, with 86 receiving Pola as a single agent and 9 patients receiving Pola combined with rituximab. Pola was well-tolerated as a single agent and in combination with rituximab, with most treatment-emergent AEs being mild, and the most common grade 3-4 AEs being neutropenia (40%), anemia (11%), or peripheral neuropathy (9%) in heavily treated patients (80% with ≥ 3 prior lines of therapy). At the recommended phase 2 dose of Pola, the ORR to monotherapy among patients with NHL (indolent B-NHL, n=16; DLBCL, n=27; MCL, n=2) was 55%, including an ORR of 56% and CR rate of 15% in patients with DLBCL.[12] In the randomized phase II ROMULUS study, patients with R/R FL or DLBCL were randomized to receive either Pola or the anti-CD22 ADC pinatuzumab vedotin (PiV) plus rituximab. Patients with R/R DLBCL who received Pola plus rituximab (n=39) had an ORR of 56% with a CR rate of 15% while patients with R/R FL had an ORR of 70% and a CR rate of 40% (n=20). Similarly, in a separate phase Ib/II study of Pola plus obinutuzumab, patients with R/R DLBCL had a best ORR of 52% and CR rate of 29% and patients with R/R FL had an ORR of 78% and CR rate of 30%. Pola has also been combined with 6 cycles of bendamustine and either rituximab or obinutuzumab in patients with R/R DLBCL or FL as part of a phase I/II study that had dose expansion and randomized cohorts (rituximab-bendamustine, BR vs Pola+rituximab-bendamustine, Pola-BR). In patients with R/R DLBCL, the best ORR and CR rate to Pola+BR in the randomized phase II portion of the study (n=40) were 70% and 57.5% as compared to 32.5% and 20%, respectively, in patients who received BR alone (n=40). The best ORR and CR rate to Pola with bendamustine and obinutuzumab were 59% and 41%, respectively. PFS and OS were significantly longer in patients who received Pola-BR, with a median OS of 12.4 months compared to 4.7 months in patients who received BR (HR 0.42; 95% CI, 0.24 to 0.75). In patients with R/R FL, the CR rate at the end of 6 cycles of Pola+BR (n=39, 69%) was similar to BR (n=41, 63%) and PFS was also similar (17 versus 17.3 months) with OS not reached in both arms.[13] Based on these findings, the FDA approved Pola plus BR for use in patients with relapsed/refractory DLBCL who have received at least two prior therapies. Pola has also been evaluated as part of initial therapy (cyclophosphamide, doxorubicin, and prednisone with either rituximab, R-CHP, or obinutuzumab, G-CHP) in a phase I study of patients with newly diagnosed DLBCL. The end of treatment ORR and CR rate after R-CHP (n=45) were 91% and 78%, respectively, and the ORR and CR rate after G-CHP (n=21) were 91% and 81%, respectively. [14] There is currently a randomized, double-blinded, placebo-controlled, phase III trial evaluating the addition of Pola to R-CHP compared to R-CHOP as initial therapy for DLBCL (POLARIX, clinicaltrials.gov: NCT03274492).

2.1.3 Rituximab with ifosfamide, carboplatin, and etoposide (R-ICE)

RICE is a standard chemo-immunotherapy regimen consisting of rituximab, etoposide, ifosfamide, and carboplatin. Rituximab is a CD20-directed cytolytic antibody. Etoposide is a topoisomerase inhibitor. Ifosfamide is a nitrogen mustard alkylating agent. Carboplatin is a platinum-based antineoplastic agent that intercalates with DNA to interfere with DNA repair. RICE is a commonly used regimen for salvage therapy before ASCT in DLBCL patients.

The dose of rituximab (375 mg/m2) is the standard approved dose for patients with previously untreated DLBCL when given in combination with CHOP (cyclophosphamide, doxorubicin, vincristine, prednisone) or other anthracycline-based chemotherapy regimens. There is no standard dose or schedule for rituximab in the relapsed or refractory setting; however, the dose (375 mg/m2) and schedule (every 3 weeks) selected in the current study have been safely and effectively employed in combination with various single- and multi-agent chemotherapy regimens for this patient population.[8, 11] The doses of ifosfamide (5000 mg/m2), carboplatin (area under the curve 5 mg/mL x min; maximum dose, 750 mg), and etoposide (100 mg/m2 per day for 3 days) are based on the original publication from Memorial Sloan Kettering Cancer Center and are the standard doses when given in a combination setting.[15]

Ifosfamide is extensively metabolized (70-86% of the dose) by CYP3A4 and CYP2B6 (Ifosfamide Prescribing Information, APP Pharmaceuticals, January 2008). Carboplatin is mainly eliminated by renal glomerular filtration (Paraplatin Prescribing Information, Bristol-Myers Squibb, July 2010). Etoposide is eliminated by multiple mechanisms, including renal and biliary excretion and several metabolic pathways (sulfation, glucuronidation, and oxidation by CYP3A4) (Etoposide Prescribing Information, Bristol-Myers Squibb, March 2011).

2.1.4 Rationale for combination of PolaR-ICE followed by Pola consolidation after ASCT in R/R DLBCL

As described above, novel treatment strategies are needed to improve outcomes for relapsed/refractory (R/R), transplant-eligible DLBCL patients, where the goal is to achieve a high-quality remission that enables subsequent ASCT. The primary unmet need is the failure to achieve a high rate of CR, as achievement of a PET-negative CR following second-line salvage therapy has been associated with improvement in outcome in relapsed DLBCL patients who proceed to ASCT.[1-3] Pola is a potent anti-CD79b ADC with demonstrated anti-tumor efficacy in R/R DLBCL and has been combined safely with chemotherapy resulting in higher response rates compared to chemotherapy alone.[16] Notably, Pola combined with BR in a population of heavily treated patients also resulted in improved PFS and OS compared to BR alone. Therefore, it has been demonstrated that Pola combined with chemotherapy can improve outcomes in patients with DLBCL. An important observation about the clinical use of Pola is that peripheral neuropathy has limited the therapeutic index of the drug, with the ultimate dose of the drug being 1.8 mg/kg as opposed to the 2.4 mg/kg dose initially chosen as the recommended phase 2 dose. In addition, the duration of Pola dosing has been limited to 6 doses, prior to the onset of dose-limiting neuropathy.

Therefore, the ideal dosing of Pola may be as a short course to improve upon the efficacy of combination chemotherapy, as demonstrated with bendamustine and CHOP in other studies. With the need for more effective bridging therapy prior to ASCT in R-R DLBCL, there is an ideal opportunity to utilize Pola as part of salvage therapy to increase the CR rate prior to ASCT. The CR rate prior to transplant is an important prognostic factor for ASCT outcome; therefore, our hypothesis is that improving salvage therapy with Pola may increase the durable response rate with a salvage/ASCT approach.

In addition, it has been demonstrated in Hodgkin lymphoma that the use of an effective ADC (brentuximab vedotin) after ASCT can improve progression-free survival. The AETHERA trial demonstrated that brentuximab vedotin consolidation treatment following ASCT prolongs PFS in patients with high risk relapsed or refractory classical Hodgkin lymphoma compared to placebo.[5] Like brentuximab vedotin in R/R Hodgkin lymphoma, Pola is an ADC that has potent anti-tumor activity in patients with R/R DLBCL. Pola has already been associated with improved survival in patients with R/R DLBCL receiving chemotherapy as compared to chemotherapy alone. [17] Therefore, we propose to use Pola as consolidation therapy after ASCT with the goal of increasing the proportion of patients with durable remission after ASCT.

2.2 Rationale for Correlative Studies

The correlative analyses that will be performed as part of this clinical trial are exploratory and intended to generate hypotheses that can be validated in a larger study. The assays described are still under development and refinement, so the exact analyses may change during the course of this study.

2.2.1 Circulating tumor DNA

The detection of circulating tumor DNA (ctDNA) has been studied in lymphoma. Next-generation sequencing (NGS)-based ctDNA detection performed by NGS of the immunoglobulin (Ig) or T-cell receptor genes can identify ctDNA in the peripheral blood mononuclear cells (PBMC) and plasma (cell-free DNA) at diagnosis in a range of lymphomas, including diffuse large B-cell lymphoma (DLBCL).[18-21] In addition, ctDNA levels correlate with treatment response in DLBCL, and the persistence or recurrence of ctDNA during and after upfront therapy is associated with subsequent DLBCL relapse. [20, 21] While the Ig-NGS method is powerful, the investigation of only Ig genes limits its sensitivity, resulting in a sizable minority of patients in whom the assay is not applicable. Meanwhile, ctDNA assessment using capture-based NGS for recurrent mutations and rearrangements has been explored in DLBCL, and the method appears feasible and highly sensitive. [22, 23] Like IgNGS, capture-based NGS MRD detection exploits the genetic features of a lymphoma to identify tumor-specific DNA in the peripheral blood of patients with lymphoma. Utilizing bioinformatics pipelines optimized for low input DNA, hybridization capturebased NGS is performed on a patient sample (i.e. peripheral blood, tumor tissue) that evaluates a panel of singlenucleotide variants (SNVs), insertions/deletions (indels), and chromosomal translocations known to be recurrently mutated in a specific lymphoma subtype (to date, primarily DLBCL). CtDNA can be quantitated by calculating the proportion of tumor-specific cfDNA molecules within a sample (the variant allele fraction). Thus far, studies have demonstrated that genetic alterations detected in ctDNA using capture-based NGS analysis of the peripheral blood are highly concordant with genetic alterations determined by NGS of a primary DLBCL tumor sample. [24-26] Similar to IgNGS, capture-based NGS based MRD detection can identify ctDNA in patients with DLBCL prior to treatment, can quantify ctDNA levels that track with treatment response and resistance, and can detect relapse prior to and at the time of clinically apparent relapse. [23-25, 27] In a study examining DLBCL patients receiving frontline or salvage therapy at several independent centers, ctDNA was detectable in 98% of patients, and pretreatment ctDNA levels and molecular responses were independently prognostic of outcomes.[28]

2.2.2 Gene expression profiling

Gene expression profiles define distinct subsets of DLBCL and are associated with outcome after standard therapy in patients with DLBCL.[29, 30] Both the cell of origin and a newer double-hit signature identify subsets of patients who have poorer outcomes with standard therapy.[31] We will study both COO and the double-hit signature in patients treated with PolaR-ICE and evaluate associations with response to therapy and PFS.

2.2.3 Mutation profiling

Recent work from multiple laboratories have studied the mutational landscape in DLBCL and identified biological clusters of mutation profiles that have prognostic significance. We will perform next-generation sequencing to evaluate the mutational landscape in patients treated with PolaR-ICE and associations with response to study treatment and PFS.[32-34]

2.2.4 Multispectral immunofluorescence

We will use the Vectra spatial multispectral immunofluorescence (mIF) system to evaluate pre-treatment and ontreatment changes in immune cell subset density and relative proximities in the tumor microenvironment.

Proof of concept that mIF is a valuable tool in studying the tumor microenvironment in lymphomas was demonstrated in Hodgkin lymphoma by the Shipp lab, where unique microenvironmental features of the HL microenvironment were elucidated.[35]

2.3 Overview and Rationale for Study Design

This is a phase 2 study of PolaR-ICE followed by ASCT and Pola consolidation in patients with relapsed or refractory (R/R) DLBCL. Adult patients with pathologically documented relapsed or refractory DLBCL after induction therapy will be enrolled. Patients with subsets of DLBCL, including mediastinal large B-cell lymphoma, transformed DLBCL, and aggressive B-cell lymphoma unclassified will not be excluded. Patients must have received anthracycline- or anthracenedione-containing induction chemotherapy. The Safety Lead-In will use a design that is slightly modified from the IQ rolling 6 design.[7] Dose level 1 will use the standard doses of R-ICE (rituximab 375 mg/m2, ifosfamide 5000 mg/m2 or 3 x 1670 mg/m2, carboplatin area under the curve 5 mg/mL x min; maximum dose, 750 mg, and etoposide 100 mg/m2 per day for 3 days) with the approved dose of Pola (1.8 mg/kg). There will be a dose deescalation dose level (dose level -1), only if necessary. Dose level -1 will use the standard doses of R-ICE with a reduced dose of Pola (1.4 mg/kg). The maximum number of PolaR-ICE cycles is 3. ASCT will be performed according to institutional standards. Patients who proceed to ASCT directly after PolaR-ICE and have achieved an objective response to PolaR-ICE will receive single-agent Pola consolidation after ASCT at the standard dose of Pola (1.8 mg/kg) every 21 days. The maximum number of Pola-containing cycles of therapy is 6.

After the tolerable dose is confirmed the study will progress to the phase 2 portion of the study, which will employ a two-stage design to evaluate the CR rate of PolaR-ICE after 2 cycles. Patients who were enrolled during the safety lead-in portion at the final dose level deemed tolerable for Phase 2 will also be included in the Phase 2 response evaluation if they are evaluable for response. At the first stage, 20 patients will be enrolled. If <8 complete responses are seen, the accrual will be terminated. If at least 8 patients achieve a complete response, the trial will continue to the second stage. At the second stage, 20 additional patients will be entered. At the end of stage 2, if 21 or more patients out of the total 40 patients experience a complete response, the combination will be considered worthy of further study.

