This is a phase 2 study of PolaR-ICE followed by ASCT and Pola consolidation in patients with relapsed or refractory (R/R) DLBCL. Adult patients with pathologically documented relapsed or refractory DLBCL after induction therapy will be enrolled. Patients with subsets of DLBCL, including mediastinal large B-cell lymphoma, transformed DLBCL, and aggressive B-cell lymphoma unclassified will not be excluded. Patients must have received anthracycline- or anthracenedione-containing induction chemotherapy. The Safety Lead-In will use a design that is slightly modified from the IQ rolling 6 design.[7] Dose level 1 will use the standard doses of R-ICE (rituximab 375 mg/m2, ifosfamide 5000 mg/m2 or 3 x 1670 mg/m2, carboplatin area under the curve 5 mg/mL x min; maximum dose, 750 mg, and etoposide 100 mg/m2 per day for 3 days) with the approved dose of Pola (1.8 mg/kg). There will be a dose de-escalation dose level (dose level -1), only if necessary. Dose level -1 will use the standard doses of R-ICE with a reduced dose of Pola (1.4 mg/kg). The maximum number of PolaR-ICE cycles is 3. Patients who proceed to ASCT directly after PolaR-ICE and have achieved an objective response to PolaR-ICE will receive single-agent Pola consolidation after ASCT at the standard dose of Pola (1.8 mg/kg) every 21 days. The maximum number of Pola-containing cycles of therapy is 6.

After the tolerable dose is confirmed the study will progress to the phase 2 portion of the study, which will employ a twostage design to evaluate the CR rate after 2 cycles of PolaR-ICE. Patients who were enrolled during the safety lead-in portion at the final dose level deemed tolerable for Phase 2 will also be included in the Phase 2 response evaluation if they are evaluable for response.

Evaluation Criteria and Endpoints

Toxicities will be will be graded using the NCI CTCAE v 5.0.

Response/progression will be assessed per 2014 Lugano classification.

Primary Endpoint(s):

- Safety Lead-in: Unacceptable toxicity (defined in Section 11.2) during the first 2 cycles of PolaR-ICE therapy.
- Phase 2: Complete response (CR) rate after 2 cycles of PolaR-ICE therapy.

Secondary Endpoint(s):

- Overall response rate (ORR) at the end of PolaR-ICE therapy.
- · Progression-free survival (PFS) and Overall survival (OS).
- CR rate after Pola consolidation among patients who were PR at ASCT.
- Toxicity of PolaR-ICE salvage therapy and toxicity of Pola consolidation after ASCT.

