5.7 Consolidation (Polatuzumab Vedotin Single-Agent)

NOTE: Participants **must meet criteria** in Section 5.7.1 to initiate Consolidation.

- See Section 5.14 regarding G-CSF administration as supportive care.
- 3-4 cycles of Pola:
 - Patients who received 2 cycles of PolaR-ICE during Salvage will receive 4 cycles of Pola Consolidation.
 - Patients who received 3 cycles of PolaR-ICE during Salvage will receive 3 cycles of Pola Consolidation.
 - The maximum number of Pola-containing cycles of therapy is 6.
- Initiate after autologous stem cell transplantation (ASCT). Stem cell mobilization and collection and ASCT will be performed per institutional standards.
- Initiate Consolidation between Day + 30 and Day + 60 post-ASCT. A delay of up to Day + 75 is permitted following consultation with the Study PI for certain criteria (see Section 5.7.1 below). Screening may initiate 21 days after ASCT.

Timing and windows for imaging are detailed in Section 10.0.

5.7.1 Criteria to Receive Consolidation Polatuzumab Vedotin

Participants must meet the below criteria to receive Consolidation therapy with single-agent Pola after completing PolaR-ICE Salvage. Criteria must be met within 28 days of starting Consolidation therapy, except where otherwise specified (labs).

	Criteria to be met in order to initiate Consolidation with polatuzumab vedotin	Action if criterion to the left is NOT met
1.	Achieved objective response per 2014 Lugano Classification at end of Salvage	Discontinue protocol therapy.
		For Grade 2 or 3:
		 Wait until toxicity improves to ≤ Grade 1.
2.	No ≥ Grade 2 peripheral neuropathy	 Administer Pola consolidation at the permanently reduced dose of 1.4 mg/kg. If patient was already at 1.4 mg/kg during salvage, discontinue protocol therapy.
		Following consultation with Study PI delay initiation of Consolidation up to Day +75 post-ASCT may be permitted.
		For Grade 4:
		Discontinue protocol therapy.
3.	Absence of unrelated toxicity not present at baseline that might adversely affect participation/ administration of polatuzumab vedotin	Discontinue protocol therapy.
4.	Recovered from ASCT toxicities	
	Including: outpatient status, able to drink and eat normally, and do not need intravenous hydration prior to Cycle 1 Day 1 of Consolidation therapy	
5.	Will initiate treatment between Day +30 and Day +60 post-ASCT	
6.	ECOG ≤ 2 within the screening period	
7.	ANC ≥ 1,000/mm³ within 14 days prior to Day 1 of Consolidation	

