7.0 DOSE DELAY / MODIFICATION GUIDELINES

7.1 Dose Delay / Modification

- o Toxicities will be graded using the NCI CTCAE v 5.0.
- o Baseline values are from the last values obtained prior to treatment.
- When attribution of a toxicity is unclear due to overlapping toxicity profiles of the drugs included in protocol therapy (e.g. hematologic, infections, febrile neutropenia), administration of R-ICE should be prioritized since it is the standard of care and as the use of polatuzumab vedotin as part of salvage therapy remains investigational. Therefore, dose reduction/delay of polatuzumab vedotin should be attempted before dose reduction/delay of agents included in R-ICE.
- o If one agent is held due to toxicity for a given cycle, administration of the delayed agent should resume once the toxicity is resolved on the same schedule with the next cycle of combination therapy.
- o If one agent is permanently discontinued, then the participant may continue with other agent(s). Refer to Section 5.6.
- If all agents are held together due to toxicity and the delay lasts > 6 weeks, then protocol therapy will be discontinued.

o Polatuzumab vedotin

- Dose delay/modification guidelines for polatuzumab vedotin-related toxicity are described in Table 7.1.
- If a delay due to toxicity lasts > 6 weeks, permanently discontinue polatuzumab vedotin.
- Doses reduced for polatuzumab vedotin-related toxicity should not be re-escalated without discussion with the Study PI.

• Dose reductions below 1.4 mg/kg are not permitted, and toxicities should be managed with dose delays or polatuzumab vedotin should be permanently discontinued.

o R-ICE

- Dose modifications for rituximab are not permitted.
- Dose modifications/ discontinuation of ifosfamide, carboplatin, and etoposide, whether or not they are due to toxicity are permitted at the investigator's discretion/ institutional standards.

Table 7.1 Dose Modifications for Polatuzumab Vedotin

Toxicity	Polatuzumab Vedotin Dose Management Guidelines
Peripheral Neuropathy	
Grade 1 Asymptomatic; clinical or diagnostic observations only; intervention not indicated	Continue at same dose level
Grade 2/3 G2:Moderate symptoms; limiting instrumental ADL G3: Severe symptoms; limiting self care ADL; assistive device indicated	Withhold until toxicity resolves to ≤ Grade 1, then resume treatment at 1.4 mg/kg See above for guidance if the participant dose is already 1.4 mg/kg.

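### If Dose Level -1 becomes the salvage dose, the plan still starts consolidation at 1.8 mg/kg, and Tables 5.3 and 7.1 disagree on the dose after neuropathy at 1.4 mg/kg has resolved

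*Combined protocol and SAP*

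**What the plan says.** **Dose by phase.** Table 5.3 makes the Phase 2 salvage dose of Pola depend on the lead-in: 1.8 mg/kg (Dose Level 1) or, if that is not tolerated, 1.4 mg/kg (Dose Level -1). The consolidation row of the same table is a flat 1.8 mg/kg. Section 2.3 agrees, with "single-agent Pola consolidation after ASCT at the standard dose of Pola (1.8 mg/kg) every 21 days", and so does the synopsis. None of the three makes the consolidation dose conditional on the salvage dose level.

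**Entry to consolidation.** Section 5.7.1 criterion 2 requires no neuropathy of Grade 2 or higher, judged within 28 days of starting consolidation. Grade 2-3 neuropathy at that check means waiting for Grade 1 or better and then giving 1.4 mg/kg, with one exception: "If patient was already at 1.4 mg/kg during salvage, discontinue protocol therapy".

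**Dose changes.** For Grade 2-3 neuropathy, Table 7.1 says "Withhold until toxicity resolves to ≤ Grade 1, then resume treatment at 1.4 mg/kg". It refers patients already at 1.4 mg/kg to the floor rule in Section 7.1: "Dose reductions below 1.4 mg/kg are not permitted, and toxicities should be managed with dose delays or polatuzumab vedotin should be permanently discontinued". On going back up, Section 7.1 says "Doses reduced for polatuzumab vedotin-related toxicity should not be re-escalated without discussion with the Study PI".

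**The concern.** Dose Level -1 opens only after 1.8 mg/kg with R-ICE has been judged intolerable, and Section 12.3 budgets for that branch (up to 48 evaluable patients). In that branch the consolidation text raises the dose for patients assigned to 1.4 mg/kg. It gives no 1.4 mg/kg starting dose for those who meet the entry criteria. Read literally, the Study PI discussion does not reach them, because their dose was assigned and never reduced for toxicity.

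The gap is sharpest for neuropathy, which Section 2.1.4 names as the toxicity that limited Pola's therapeutic index. A patient can have Grade 2-3 neuropathy at 1.4 mg/kg during salvage and recover before the consolidation check. Sites then have two tables that point different ways. At stake is consistent and safe dosing of individual patients.

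**Working it through.** The plan states no figure on this point, so there is none to reproduce. The check is dose arithmetic, then a side-by-side reading of the rules.

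**1. Planned Pola exposure.** Inputs: 1.8 and 1.4 mg/kg (Table 5.3); 2 salvage + 4 consolidation cycles or 3 + 3, six at most (Section 5.7). No missed doses are assumed.

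- Step up per dose: 1.8 / 1.4 = 1.286, a rise of 0.4 mg/kg or 28.6%.
- Dose Level 1 throughout: 6 × 1.8 = 10.8 mg/kg.
- Dose Level -1 as written, 2 + 4: 2 × 1.4 + 4 × 1.8 = 10.0 mg/kg.
- Dose Level -1 as written, 3 + 3: 3 × 1.4 + 3 × 1.8 = 9.6 mg/kg.
- 1.4 mg/kg carried forward: 6 × 1.4 = 8.4 mg/kg.
- Share of the reduction undone: (10.0 − 8.4) / (10.8 − 8.4) = 0.67 for 2 + 4, and (9.6 − 8.4) / 2.4 = 0.50 for 3 + 3.

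**2. A Dose Level -1 patient with Grade 2-3 neuropathy in salvage.**

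| Neuropathy at the consolidation check | Rule applied | Result |
|---|---|---|
| Still Grade 2-3 | 5.7.1 criterion 2 | Protocol therapy discontinued |
| Resolved to Grade 1 or better | 5.7.1 criterion 2 is met, then Table 5.3 | 1.8 mg/kg |
| Resolved to Grade 1 or better | Table 7.1, which is not limited to salvage | 1.4 mg/kg, or delay or stop under the floor rule |

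Consolidation starts on Day +30 to +60 after ASCT, so there is time for neuropathy to resolve. Under 5.7.1 with Table 5.3, the same history leads to discontinuation or to a higher dose, depending on when it resolves. Under Table 7.1 it never leads to a higher dose. The text does not say which table governs.

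**3. How likely the branch is.** The documents give no true unacceptable-toxicity rate, so p is assumed. The floor counts only 3 or more events in 8 patients. With slow accrual, Dose Level 1 fails on 2 or more events in the first 6, or on 1 in 6 followed by 2 in the next 2. At p = 0.10 the slow-accrual figure is [1 − 0.9^6 − 6(0.1)(0.9^5)] + 6(0.1)(0.9^5)(0.1^2) = 0.114 + 0.004 = 0.118.

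| Assumed p | Floor (3+/8) | Slow accrual |
|---|---|---|
| 0.10 | 0.038 | 0.118 |
| 0.20 | 0.203 | 0.360 |
| 0.33 | 0.524 | 0.671 |

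**4. How many patients.** If Dose Level -1 accrues 40 patients and half reach ASCT, as in the randomized R-ICE versus R-DHAP trial described in Section 2.1.1, about 20 could start consolidation (ceiling 40). The documents give no rate of Grade 2-3 neuropathy for 2 to 3 doses at 1.4 mg/kg. At an assumed 5% to 20% with resolution, 20 × 0.05 = 1 to 20 × 0.20 = 4 patients would meet the conflict, given that the branch opens. Weighted by its chance of opening at p = 0.10 to 0.20, this is 1 × 0.04 = 0.04 to 4 × 0.36 = 1.4 patients.

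**The case against.** The fixed 1.8 mg/kg looks deliberate. The same table ties the salvage dose to the lead-in and leaves consolidation fixed, and Section 12.5 expects consolidation patients from any dose level. Failure of the five-drug combination does not show that Pola alone at 1.8 mg/kg after transplant is intolerable. Patients treated at 1.4 mg/kg were also considered: Section 5.7.1 stops them if Grade 2-3 neuropathy is present at the check, which is stricter than the rule for 1.8 mg/kg patients. As-written totals stay below the Dose Level 1 plan. All of this stands.

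A reader might go further and infer that the plan directs 1.8 mg/kg after resolved Grade 2-3 neuropathy at 1.4 mg/kg. The documents do not support that. Table 7.1 offers 1.4 mg/kg, delay or discontinuation and never a rise, so what is shown is a conflict between tables.

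Nor is it right that nothing checks these patients. There are 17 entry criteria, examination and adverse event assessment at the first consolidation visit, the investigator's power to stop treatment, reductions to 1.4 mg/kg during consolidation, and the group stopping rule in Section 12.5. What is missing is a stated starting dose and a specific Study PI discussion. For neuropathy, the in-consolidation reduction acts only after a new Grade 2-3 event, and the Section 12.5 rule starts at 6 patients and sets no individual dose.

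Nor does every consolidation patient step up. Lead-in patients treated at Dose Level 1 were assigned 1.8 mg/kg in salvage.

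**Conclusion.** The point holds in a narrow form and is minor. For patients assigned to Dose Level -1 who meet Section 5.7.1, the default text raises Pola by 28.6% per dose and undoes half to two thirds of the planned reduction. It states no 1.4 mg/kg start, and the Study PI discussion does not literally apply. For those whose Grade 2-3 salvage neuropathy has resolved by the consolidation check, Tables 5.3 and 7.1 need reconciling.

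It matters only if Dose Level -1 opens. The primary endpoint, CR after two salvage cycles, is measured before consolidation, so type I error and power are unaffected. The exposure figures follow from the protocol's doses and cycles. The probabilities and patient counts rest on assumed rates and show scale only. The documents do not show that 1.8 mg/kg is the wrong dose for Dose Level -1 patients without such neuropathy.

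**What to change.** In Table 5.3, Section 5.7.1 and Section 7.1, with matching text in the synopsis and Section 2.3:

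- State that a patient who had Grade 2 or higher neuropathy at 1.4 mg/kg in salvage, since resolved to Grade 1 or better, starts consolidation at 1.4 mg/kg and is not raised to 1.8 mg/kg without Study PI agreement.
- Extend the Study PI discussion in Section 7.1 to any patient whose last salvage dose was 1.4 mg/kg, whether assigned or reduced.
- Leave the Section 5.7.1 discontinuation rule for neuropathy still present at the check as it is.
- If 1.8 mg/kg is intended for the other Dose Level -1 patients, add one sentence of rationale to Section 2.3.

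The change is to wording only and adds no patients, procedures or analyses. It costs one Study PI discussion per affected patient. Some patients may receive less consolidation Pola (8.4 instead of 9.6 to 10.0 mg/kg in total), with possible loss of activity. Some mixing of consolidation doses would slightly blur the secondary endpoint of CR after consolidation among patients in PR at ASCT.
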